6.3. Safety Measurements

The following safety assessments will be done during the study:

- Incidence and intensity of AEs evaluated using the CTCAE version 4.03
- Incidence and intensity of clinically significant abnormal laboratory values evaluated using the CTCAE version 4.03
- Percentage of patients experiencing dose adjustments, including delays or discontinuation of study medication
- Physical examination findings
- Vital signs measurements
- ECG (including PR, QRS, QT, QTc and RR intervals) findings

6.4. Pharmacokinetic Measurements

PK will be performed on patients enrolled in the run-in phase.

- PK blood samples will be taken immediately pre-infusion then at 2, 3, 4, 6, 10, 21 and 24 hours after start of infusion on Days 1 and 8 of Cycles 1, 2 and 3 (time window at each sample collected: \pm 5 min).
- Blood samples will be collected, using 10 mL sodium heparin Vacutainer® tubes. The tube will be gently inverted to ensure adequate mixing of the blood sample and anticoagulant. Samples will be placed on ice until separation and must be centrifuged within 20 minutes of collection. A precise record of blood sample collection times must be maintained on the appropriate source document.
- Plasma samples will be analyzed via a validated high performance liquid chromatography/tandem mass spectrometry (HPLC/MS-MS) method for SCB01A.

6.5. Bioanalytical Measurements

Exploratory research will be performed to analyze relevant biomarkers and the correlation with clinical outcome.

- Biomarkers analysis will be performed on patients enrolled in the run-in phase, including CEC, VEGF and CEP cells)
- Tumor micro vessel density and blood flow by DCE-MRI will be performed in the patients with identified sites at both baseline and at 6 hours after the infusion of the drug on C1D1
- HPV status (expression of p16 by immunohistochemistry [IHC]) at baseline for all patients

6.6. Health outcomes measurements

The following health outcomes assessments will be completed by patients (see Section 11.3 [Appendix 4]):

- EORTC QLQ-C30), version 3;
- EORTC QLQ-H&N35

Health outcomes assessments will be performed at screening and all clinic visits (before study drug administered, where applicable, except at C1D1)

7. Adverse Events Definitions and Reporting

7.1. Adverse Events

An AE is any untoward medical occurrence that occurs in a patient or clinical investigation patient administered a pharmaceutical product, and which does not necessarily have to have a causal relationship with this treatment. An AE can therefore be any unfavorable and unintended sign (including abnormal laboratory finding), symptom, or disease temporally associated with the use of an IP, whether or not considered related to the medicinal product (definition per ICH E2A and E6 R1).

All AEs, regardless of seriousness, severity, or presumed relationship to study therapy, must be recorded using medical terminology on the AE eCRF page. Whenever possible, diagnoses should be given when signs and symptoms are due to a common etiology (e.g., cough, runny nose, sneezing, sore throat, and head congestion should be reported as “upper respiratory infection”). All measures required for AE management must be recorded in the source document and reported according to Sponsor instructions.

For all AEs, the Investigator must pursue and obtain information adequate to both determine the outcome of the AE and to assess whether it meets the criteria for classification as an SAE (see Section on SAEs) requiring immediate notification to the Sponsor or its designated representative. For all AEs, sufficient information should be obtained by the Investigator to determine the causality of the AE.

Interventions for pre-treatment conditions (e.g., elective cosmetic surgery) or medical procedures that were planned before study enrolment are not considered AE.

7.1.1. Intensity Assessment

The severity of the AE will be graded according to the NCI Common Terminology Criteria for AEs (CTCAE) Grading Scale Version 4.03 (Publish Date: May 28, 2009, <http://ctep.cancer.gov/reporting/ctc.html>).

The maximum severity (intensity) of the AE will be categorized by the Investigator as follows:

Grade 1	Mild; asymptomatic or mild symptoms; clinical or diagnostic observations only; intervention not indicated
Grade 2	Moderate; minimal, local or non-invasive intervention indicated; limiting age-appropriate instrumental activities of daily living
Grade 3	Severe or medically significant but not immediately life-threatening; hospitalization or prolongation of hospitalization indicated; disabling; limiting self-care activities of daily living.
Grade 4	Life-threatening consequences; urgent intervention indicated
Grade 5	Death related to AE

For AEs not covered by NCI CTCAE, the severity will be characterized as “mild,” “moderate,” or “severe” according to the following definitions:

- Mild events are usually transient and do not interfere with the patient’s daily activities
- Moderate events introduce a low level of inconvenience or concern to the patient and may interfere with daily activities
- Severe events interrupt the patient’s usual daily activities.

When changes in the intensity of an AE occur more frequently than once a day, the maximum intensity for the experience should be noted. If the intensity category changes over a number of days, then those changes should be recorded separately (with distinct onset dates). All AEs, due to any cause that occurs during the investigation, whether or not related to the study drug, should be reported to the Safety Coordinator.

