7.2. Adverse Event Reporting

All AEs occurring during the study (from the time of informed consent obtained until 28 days after the last dose of study treatment) observed by the Investigator or reported by the patient (whether or not attributed to study drug), will be reported on the eCRF. Clinically significant AEs considered related or non-related to the IP by the Investigator or the Sponsor will be followed until resolved or considered stable by the Investigator. The following information must be provided: description; dates of onset and resolution; severity; assessment of relatedness to IP, other suspect drug, or device; and action taken. The investigator may be asked to provide follow-up information.

All AEs, serious or not, that result in the patient's permanent withdrawal of IP or from the study will be discussed between the investigator and medical monitor. The eCRF for EOT/Early Withdrawal Visit should be completed including reason of withdrawal.

It will be the investigator's clinical judgment whether or not an AE is of sufficient severity to require the patient's removal from study treatment. A patient may also voluntarily withdraw from study treatment due to what he or she perceives as an intolerable AE. If either of these occurs, the patient must undergo EOT assessment and be given appropriate care under medical supervision until symptoms cease or the condition becomes stable.

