8.4. Safety Analysis

Safety profile will be evaluated by the following endpoints.

- Hematology, clinical chemistry, coagulation factors and urinalysis laboratory data changes
- AE incidence/SAE incidence
- Physical examination result changes
- Vital sign changes
- Electrocardiogram (ECG) (including PR, QRS, QT, QTc, and RR intervals) results

All safety endpoint data will be listed and summarized for each dose and day within cycle using descriptive statistics. The change from baseline data for the safety endpoints will also be summarized using descriptive statistics.

Number and percentage of patients experiencing at least one DLT or AE will be tabulated by dose. Further details regarding any DLTs or AEs experienced will be provided in data listings. All recorded AEs will be listed and tabulated by system organ class and preferred term using the Medical Dictionary for Regulatory Activities (MedDRA) and by dose level. The incidence of Treatment Emergent AEs (TEAEs) during the study period will be tabulated by dose group, body system, and preferred term. TEAEs are those events that occur or worsen on or after first dose of IP and up to 28 days after the last dose. TEAEs are AEs with onset dates on or after the first dosing date. Those with missing onset dates will be included as treatment emergent. Number and percentage of patients who withdrew/stopped dosing will be tabulated. Number and percentage of patients who missed 1 or more doses (1 dose, 2 doses, etc.) in any cycle will be tabulated by cycle.

Serious AEs, Grade 3 and above AEs, AEs related to study treatment, and AEs causing discontinuation will be tabulated. AEs for individual patients will be listed, along with information regarding onset, duration, severity, and relationship to study treatment.

Vital signs, physical examination, ECG, and clinical laboratory test results will be listed and summarized by dose group, cycle and day within cycle as applicable and may be presented graphically. Any significant or outside normal range limits value for vital signs, physical examination, ECG, or clinical laboratory results will be listed

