9.1. Adverse Events

Adverse events (AEs) will be coded using the Medical Dictionary for Regulatory Activities (MedDRA®, Version 19.1 or higher), and data will be summarized by System Organ Class (SOC) and Preferred Term (PT). The number and percent of subjects reporting each AE will be summarized for each dose level (cohort) and overall. A subject with two or more AEs within the same level of summarization (i.e., SOC or PT) will be counted only once in that level using the most severe (i.e., highest severity/grade) event or most related (for the relationship to study drug table). Percentages will be based on the number of subjects in the Safety Population within each dose level (cohort). The number of AEs reported will also be presented.

Treatment-emergent AEs (TEAEs) are defined as pre-treatment existing conditions that worsen after study drug administration, or events that occur during the course of the study during or after administration of study drug. Only TEAEs will be included in the AE summary tables which will present data by dose level (cohort). The cohorts to be included in each table are listed in section 3. In the case of a missing AE start date or stop date, the most conservative approach will be followed to classify AE into TEAE.

An overall summary of AEs will be produced including the number of TEAEs; the number and % of subjects reporting at least one: TEAE, serious TEAE, Dose Limiting Toxicity (DLT), grade 3 or higher TEAE, TEAE related to study treatment (possibly, probably, or definitely related), serious TEAE related to study treatment, grade 3 or higher TEAE related to the study drug, TEAEs by maximum severity and TEAEs by maximum relationship.

Additional AE tables will be generated as follows:

- TEAEs by SOC and PT
- Study Medication Related TEAEs by SOC and PT
- TEAEs by (Maximum) Severity
- TEAEs by (Maximum) Relationship to Study Medication
- Grade 3 or Higher TEAE by SOC and PT
- Treatment Emergent SAEs
- Study Medication Related SAEs by SOC and PT
- Dose Limiting Toxicity (DLT) by SOC and PT
- TEAEs Leading to Study Medication Permanently Discontinued
- TEAEs Leading to Study Medication Interrupted
- TEAEs Leading to Death
- Duration from Last Dosing to the Start of TEAE (days of each TEAE since its immediate last dosing)

A by-subject AE data listing, including verbatim term, MedDRA SOC and PT, severity, outcome and relationship to study treatment, will be provided. A separate listing will be generated for SAEs.

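### Grade changes over days become separate AE records, and no rule rejoins them before TEAEs are counted and timed; Protocol 8.4 and SAP 9.1 also leave unclear whether an improving pre-dose AE is treatment-emergent

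*Protocol*

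**What the plan says.** **Recording.** Protocol 7.1.1 (Intensity Assessment) says: "If the intensity category changes over a number of days, then those changes should be recorded separately (with distinct onset dates". Faster fluctuation is treated differently: "When changes in the intensity of an AE occur more frequently than once a day, the maximum intensity for the experience should be noted". Protocol 7.2 collects AEs "from the time of informed consent obtained until 28 days after the last dose of study treatment", so an AE record can exist before any study drug is given.

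**Definition of a TEAE.** Protocol 8.4 (Safety Analysis) gives two sentences. The first is "TEAEs are those events that occur or worsen on or after first dose of IP and up to 28 days after the last dose". The second is "TEAEs are AEs with onset dates on or after the first dosing date", with no condition about worsening. SAP 9.1 (Adverse Events) also has two parts. One covers "pre-treatment existing conditions that worsen after study drug administration". The other covers anything arising in the study once dosing has begun.

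**Counting and timing.** SAP 9.1 counts a subject once per SOC or PT, at the worst grade. It adds: "The number of AEs reported will also be presented". The overall summary includes the number of TEAEs, and one further table is "Duration from Last Dosing to the Start of TEAE (days of each TEAE since its immediate last dosing". SAP section 18 marks Tables 14.3.2.1, 14.3.2.2, 14.3.2.3 and 14.3.2.13 to be produced.

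Neither document says how several records of one episode are to be joined.

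**The concern.** Under the recording rule, one episode can sit in the database as several rows, and every row after the first has an onset date that is really the date of a grade change. Two consequences follow.

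1. **Event counts and timing.** A programmer who follows SAP 9.1 as written counts rows as TEAEs and measures the interval from last dose for each row. The number of TEAEs then depends on how often grades moved as well as on how many events occurred. Table 14.3.2.13 mixes true onsets with dates of worsening and of recovery.

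2. **TEAE status.** If an AE recorded before dosing improves afterwards, the improved-grade row has a post-dose onset date. The second sentence of Protocol 8.4 admits that row as a TEAE. The first sentence, and the first part of the SAP definition, would not.

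SAP section 1 says the analysis will concentrate on safety because only five subjects were enrolled. These tables are therefore a main output of the study, and at that size a single row is visible.

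**Working it through.** The documents state no figure that depends on these rules, so there is nothing to reproduce. The check applies the written rules to three hypothetical AE histories (assumed, not trial data).

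**Inputs**
- One row per grade change on different days: Protocol 7.1.1.
- First dose on Day 1, second on Day 8: Protocol Tables 1 and 2.
- Five subjects enrolled, in the 3.25 and 12 mg/m² cohorts only: SAP sections 1 and 2.1.

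**TEAE counts**

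| History | Rows | TEAE rows by onset date alone | TEAE episodes if records are linked and pre-dose events must worsen | Subjects (onset date / linked) |
|---|---|---|---|---|
| A. New after dosing, grades 1-2-3-2-1 on different days | 5 | 5 | 1 | 1 / 1 |
| B. Pre-dose grade 2, improves to 1 after dosing | 2 | 1 | 0 | 1 / 0 |
| C. Pre-dose grade 1, worsens to 2, returns to 1 | 3 | 2 | 1 | 1 / 1 |

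History A shows the general rule. A new episode that passes through k grade levels on different days gives k TEAEs but still one subject. History C shows the same duplication for a pre-dose event that truly worsens. Only history B changes a subject count.

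**Timing, history A.** Assume grade changes on Days 3, 5, 7, 9 and 12, and take the interval as record date minus the date of the last preceding dose.
- Rows on Days 3, 5 and 7 follow the Day 1 dose: 3 − 1 = 2, 5 − 1 = 4, 7 − 1 = 6 days.
- Rows on Days 9 and 12 follow the Day 8 dose: 9 − 8 = 1, 12 − 8 = 4 days.
- Mean over five rows: (2 + 4 + 6 + 1 + 4)/5 = 17/5 = 3.4 days. The single true onset is 2 days after dosing.

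The last two rows mark recovery, yet they enter the table as events starting 1 and 4 days after the second dose.

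**Incidence, history B.** If such a row were classed as a TEAE and the subject had no other TEAE of that term:
- Overall: 1/5 = 20 percentage points, if all five enrolled subjects were dosed.
- By cohort: the split is not stated. The Protocol synopsis says the first dose level was completed, which implies at least three subjects there, and SAP section 2.1 implies at least one at the second. With 3/2 the effect is 1/3 = 33 or 1/2 = 50 points. With 4/1 it is 1/4 = 25 or 1/1 = 100 points.

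**Reading the definitions together for history B**
- Protocol 8.4, first sentence: the event neither began nor worsened after dosing, so it is not a TEAE.
- Protocol 8.4, second sentence: the row's onset date is after first dosing, so it is a TEAE.
- SAP 9.1, first part: a pre-treatment condition that did not worsen, so it is not a TEAE.
- SAP 9.1, second part: a TEAE only if the grade-change row is taken as an event in its own right, which the SAP does not settle.

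**The case against.** The strongest reply is that the SAP already guards what matters most. Each subject is counted once per SOC or PT at the worst grade, so split rows of a genuine post-dose event cannot raise incidence or distort maximum severity. That stands.

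A reader might infer that the SAP classifies every row by its onset date, so that improving symptoms automatically become TEAEs and patient-level incidence is inflated throughout. The documents do not support this. The onset-only sentence is in Protocol 8.4, not in the SAP. Protocol 8.1 leaves the detailed methods to the SAP, and the first part of the SAP definition requires a pre-treatment condition to worsen. On a natural reading it excludes history B. What remains is an ambiguity in the second part of the definition and an unreconciled sentence in the Protocol.

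Nor does every grade change make a new row, since changes more frequent than daily are noted only at their maximum. The exposed group is also narrow. Protocol 5.1.1 records symptoms from the 30 days before screening as medical history, and a symptom held only there has no AE row to split. An improving pre-dose event would reach Table 14.3.2.3 only if judged at least possibly related.

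Finally, the stakes are modest. The analysis is descriptive, makes no formal comparison between doses, and covers five subjects. Listing 16.2.7.1 is marked to be produced, so a careful reader may be able to trace split rows. That limits the harm but does not correct the tables. None of these replies touches the event counts or Table 14.3.2.13.

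**Conclusion.** The point holds in two parts of different strength.

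- **Follows directly from the text:** without a linking rule, event counts include grade changes over days, and Table 14.3.2.13 receives one start per row. A 1-2-3-2-1 episode gives 5 TEAEs and 5 starts where there was one event and one onset. How often this occurred in the five subjects is unknown.
- **Conditional:** the definitions conflict on an AE first recorded between consent and first dose that later improves. If such a row were classed as treatment-emergent, and the subject had no other TEAE of that term, overall incidence of the term would rise by 20 points (all five dosed). The rise within a cohort would be 33 or 50 points under a 3/2 split, or 25 or 100 under 4/1.

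Subject-level incidence and maximum severity of genuinely new events are sound as planned. This is a gap in derivation rules that should be closed before the safety tables are produced. It does not invalidate the safety analysis.

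**What to change.** Add one paragraph to SAP 9.1:

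1. **Link records.** Join rows of the same subject and preferred term when one starts on, or the day after, the previous stop date. Have the linked rows reviewed so that true recurrences are not merged. Count the episode once, at its maximum grade, wherever a number of events is shown.
2. **Settle TEAE status.** An episode that began before dosing is a TEAE only if a post-dose grade exceeds the last pre-dose grade. State that this rule governs over the onset-only sentence in Protocol 8.4.
3. **Define the start used in Table 14.3.2.13.** For new events, use the first post-dose onset. For pre-dose events that worsen, use the date of first worsening above the pre-dose grade, because their first onset precedes every dose and the interval would be undefined. Leave out rows that mark only improvement. If the timing of a later worsening is of interest, show it separately, so that it is not attributed to the dose before the first onset.
4. **Keep all original rows** in Listing 16.2.7.1.

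The cost is a short derivation and some review of the linked records. No new data are needed, and nothing about patient management changes.

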7.1.2. Causality Assessment

- **Unrelated:** The AE is clearly related to other causes such as participant’s clinical state, environmental factors, or other therapies administered.
- **Unlikely to be related:** The AE does not follow a reasonable temporal sequence from study drug administration; could readily have been produced by other causes such as the participant’s clinical state, environmental factors, or other therapies administered; does not follow a known response pattern to the study drug.
- **Possibly related:** The AE follows a reasonable temporal sequence from study drug administration; follows a known response pattern to the study drug; could

readily have been produced by other causes such as the participant's clinical state, environmental factors, or other therapies administered.

- **Probably related:** The AE follows a reasonable temporal sequence from study drug administration; follows a known response pattern to the study drug; cannot be reasonably explained by other factors such as the participant's clinical state, environmental factors, or other therapies administered; improvement upon cessation of test drug.
- **Definitely related:** The AE follows a reasonable temporal sequence from study drug administration; follows a known response pattern to the study drug; cannot be reasonably explained by other factors such as the participant's clinical state, environmental factors, or other therapies administered; improvement upon cessation of test drug or reappears upon repeat exposure (if rechallenge occurs).

7.2. Adverse Event Reporting

All AEs occurring during the study (from the time of informed consent obtained until 28 days after the last dose of study treatment) observed by the Investigator or reported by the patient (whether or not attributed to study drug), will be reported on the eCRF. Clinically significant AEs considered related or non-related to the IP by the Investigator or the Sponsor will be followed until resolved or considered stable by the Investigator. The following information must be provided: description; dates of onset and resolution; severity; assessment of relatedness to IP, other suspect drug, or device; and action taken. The investigator may be asked to provide follow-up information.

All AEs, serious or not, that result in the patient's permanent withdrawal of IP or from the study will be discussed between the investigator and medical monitor. The eCRF for EOT/Early Withdrawal Visit should be completed including reason of withdrawal.

It will be the investigator's clinical judgment whether or not an AE is of sufficient severity to require the patient's removal from study treatment. A patient may also voluntarily withdraw from study treatment due to what he or she perceives as an intolerable AE. If either of these occurs, the patient must undergo EOT assessment and be given appropriate care under medical supervision until symptoms cease or the condition becomes stable.

7.3. Serious Adverse Events (SAEs)

An SAE is defined as any untoward medical occurrence that at any dose (ICH E2A and E6 R1):

- Results in death.
- Is life-threatening.
- This means that the patient is at risk of death at the time of the event; it does not mean that the event hypothetically might have caused death if it were more severe.
- Requires inpatient hospitalization or prolongation of existing hospitalization.
- Results in persistent or significant disability or incapacity.

- Is a congenital anomaly or birth defect.

Other important medical events that may not be immediately life-threatening or result in death or hospitalization, based upon appropriate medical judgment, are considered SAEs if they are thought to jeopardize the patient and/or require medical or surgical intervention to prevent one of the outcomes defining a SAE.

Since SAEs are critically important for the identification of significant safety problems, it is important to take into account both the Investigator's and the sponsor's assessment. If either the sponsor or investigator believes that the event is serious, the event must be considered serious and evaluated by the Sponsor for expedited reporting.

All SAEs must be reported to the sponsor or sponsor designee immediately after the Investigator becomes aware of the event, along with a determination as to whether it is associated with the IP or any other study procedure.

Disease progression should not be recorded as an AE or SAE term; instead, signs and symptoms of clinical sequelae resulting from disease progression will be reported if they fulfil the SAE definition.

